### **7.3.3. Additional Analyses of the Primary Safety Endpoint**

The outcomes in the primary safety endpoint will also be analyzed individually. A sensitivity analysis using the PP population will also be performed.

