Treatment Description	All eligible participants will initiate IS withdrawal. Approximately 10-12 weeks after initiating IS withdrawal, subjects will have autologous Tregs collected for darTregs manufacturing. 
During the last 2 weeks of IS withdrawal Step 2 (CNI reduced by 25%), a single total dose of 400 x 10^6 ± 100 deuterium-labeled darTregs will be infused intravenously. The subject will then, if eligible, resume IS withdrawal within 2 weeks after darTregs infusion (see Section entitled "Resumption of IS Withdrawal after darTregs Infusion" below). Only subjects who receive 300-500 x 10^6 darTregs and who meet the primary endpoint of 75% reduction in CNI from baseline after darTregs will be offered the opportunity to continue IS withdrawal until complete discontinuation of IS (secondary endpoint). Those who receive 100-300 x 10^6 darTregs will only be allowed to proceed to the primary endpoint but will not be eligible for complete IS withdrawal.

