#### 4. ANALYSIS SAMPLES

The summary descriptive analyses will be performed on the following subject populations:

1. All subjects who give informed consent and undergo the screening liver biopsy (Safety Sample).
2. The Intent-to-treat I sample (ITT1) will be defined as all subjects who initiate IS withdrawal
3. The Intent-to-treat II sample (ITT2) will be defined as all subjects who receive darTregs.
4. The Per-Protocol sample (PP) will be defined as all subjects who receive at least 300 x 10^6 cells of darTregs.

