### 6.2. Treatment Adherence

A summary of each subject's adherence to the tapering schedule will be presented in graphical form, with indications for pauses at each level and any deviations from the recommended dose at each taper level.

A summary of the number of cells infused will be presented for the darTregs as well as a categorical summary of the number of subjects that received between 100 and  $300 \times 10^6$  cells of darTregs, and the number of subjects that received at least  $300 \times 10^6$  cells of darTregs.

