## **7.3. Primary Safety Endpoint**

The primary safety endpoint is a descriptive analysis of three outcomes assessed 24 weeks after darTregs:

- CTCAE Grade 3 or higher AEs attributable to the darTregs infusion including infusion reaction / cytokine release syndrome
- study defined Grade 3 or higher infections (Protocol section 14.3.1)
- any malignancy, including PTLD

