### **7.3.1. Computation of the Primary Safety Endpoint**

All subjects who have any of the listed outcomes above will be counted as meeting the primary safety endpoint.

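### The only sensitivity set for the primary safety endpoint is defined by cells received, so an infusion reaction that cuts the dose short can remove its own case from that analysis

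*SAP*

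**What the plan says.** **Analysis sets (SAP Section 4).** ITT1 is everyone who starts immunosuppression withdrawal. For the infused subjects, "The Intent-to-treat II sample (ITT2) will be defined as all subjects who receive darTregs", with no minimum cell number. For the third set, "The Per-Protocol sample (PP) will be defined as all subjects who receive at least 300 x 10 6 cells of darTregs".

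**Endpoint (SAP Sections 7.3 and 7.3.1).** The first of three components, assessed 24 weeks after infusion, is "CTCAE Grade 3 or higher AEs attributable to the darTregs infusion including infusion reaction / cytokine release syndrome". The other two are study-defined Grade 3 or higher infections and any malignancy. One component is enough: "All subjects who have any of the listed outcomes above will be counted as meeting the primary safety endpoint".

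**Analyses (SAP Sections 7.3.2 and 7.3.3).** The primary analysis is an exact binomial proportion with an exact 95% interval in ITT1. Section 7.3.3 adds an analysis of each component and then one alternative population: "A sensitivity analysis using the PP population will also be performed". ITT2 is not named for this endpoint, although Sections 7.2.3 and 7.4 use it for efficacy.

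**Dose (SAP Sections 1 and 6.2).** The synopsis plans "a single total dose of 400 x 10 6 ± 100 deuterium-labeled darTregs", that is 300 to 500 x 10^6. Section 6.2 will tabulate cells infused, including "the number of subjects that received between 100 and" 300 x 10^6, so the plan foresees subjects below the PP threshold.

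**The concern.** The number of cells received is known only when the infusion ends, and a severe reaction during the infusion can reduce it. PP membership can therefore depend on the outcome that the PP analysis counts. A subject whose infusion is stopped below 300 x 10^6 cells for a Grade 3 or higher reaction has the endpoint event and, through that same event, fails the membership rule. Section 4 has no provision that keeps such a subject in PP.

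What is at stake is the reading of one descriptive analysis. Because ITT1 includes subjects who start withdrawal but are never infused, a reader who wants the event rate among treated subjects will turn to PP, the only infused-only set named for the endpoint. A low PP rate could then seem to support safety at the target dose when part of the reason is that a dose-limiting reaction was excluded.

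**Working it through.** The SAP states no figure on this point, so there is none to reproduce. The check applies the SAP's own method, the exact interval, to an assumed case.

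**Inputs**
- PP threshold: 300 x 10^6 cells received (Section 4).
- Planned dose: 300 to 500 x 10^6 (synopsis, Treatment Description).
- Number infused, n: 11, the accrual target in the synopsis, assuming all are infused. The Study Duration entry of the synopsis mentions nine, so n = 9 is shown as well.
- Number in ITT1: 18, an assumed upper limit in which every enrolled subject starts withdrawal.
- Number of infusions stopped below the threshold by a qualifying reaction, k: assumed. The SAP gives no frequency.

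**Step 1: when a stopped infusion falls below the threshold.** The fraction of the product that must be delivered to stay in PP is 300/dose (doses in 10^6 cells).
- 300: 300/300 = 100%
- 400: 300/400 = 75%
- 500: 300/500 = 60%

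A stop after that point leaves the subject in PP.

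**Step 2: direction.** Let x of n infused subjects have the endpoint. Removing one subject who has it changes the rate from x/n to (x - 1)/(n - 1). The difference is x/n - (x - 1)/(n - 1) = (n - x)/[n(n - 1)], which is positive whenever x < n. For x = 1 and n = 11 it is 10/110 = 9.1 percentage points. Exclusion for a dose-limiting reaction therefore never raises the rate.

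**Step 3: size.** The exact 95% limits are the 2.5% quantile of Beta(x, n - x + 1) and the 97.5% quantile of Beta(x + 1, n - x). For x = 0 the lower limit is 0 and the upper limit is 1 - 0.025^(1/n). For example, 1 - 0.025^(1/10) = 30.8%.

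| Assumed case | All infused (ITT2) | PP |
|---|---|---|
| n = 11, k = 1 | 1/11 = 9.1% (0.2-41.3%) | 0/10 = 0% (0-30.8%) |
| n = 11, k = 2 | 2/11 = 18.2% (2.3-51.8%) | 0/9 = 0% (0-33.6%) |
| n = 9, k = 1 | 1/9 = 11.1% (0.3-48.2%) | 0/8 = 0% (0-36.9%) |
| n = 11, k = 0 | no change from this cause | no change from this cause |

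**Step 4: the primary analysis in the same case.** ITT1 keeps the event. With 18 subjects in ITT1, one case gives 1/18 = 5.6% (0.1-27.3%).

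**Step 5: exclusions for other reasons.** If one subject without the event falls below 300 x 10^6 because of product yield, and the one event is not dose-limiting, the PP rate rises from 1/11 = 9.1% to 1/10 = 10.0% (0.3-44.5%). The downward direction therefore belongs to dose-limiting reactions, not to PP in general.

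**The case against.** **The event stays visible.** ITT1 retains the subject, and Section 7.3.3 also analyses each component separately. Section 8.2 lists Grade 3 or higher infusion reactions among the events of interest in the safety sample, and also tabulates events leading to study drug discontinuation. Section 5.1 reports reasons for stopping study treatment early. Under the synopsis, attributable Grade 3 or higher events in two subjects pause the study for DSMB review. All of this stands. A reader might infer that the plan hides severe infusion reactions or biases its primary safety result; the SAP does not support either.

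**The trigger is not in the SAP.** No section describes stopping an infusion for a reaction; the protocol, which is not shown, may do so. Section 6.2 gives no cause for the lower dose category, so it is not evidence that reactions produce low doses. This stands too: the table above shows what would happen, not what is likely.

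**The affected set is narrow.** The reaction must occur during the infusion and stop it before the threshold. Later reactions, infections and malignancy do not change PP membership. A reader might take the PP rate to be always too low, or always below the primary rate. Step 5 shows the first is wrong. For the second, one event that does not limit the dose can give 1/11 = 9.1% in PP against 1/18 = 5.6% in ITT1.

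**The analysis is descriptive.** There is no test or decision rule, and the intervals overlap almost entirely. Safety at the target dose is also a legitimate question.

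These points limit the weight of the concern but do not remove it: a set whose membership the outcome can change is a poor choice as the sole alternative population for that outcome.

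**Conclusion.** The point holds in a limited form. As defined, PP can lose a subject because of the infusion reaction being counted, and for such dose-limiting reactions the PP rate can only fall. One case among 11 infused takes the estimate from 9.1% to 0%. The size rests on assumed numbers of infused subjects and stopped infusions, and it is nil if no infusion stops below 300 x 10^6 cells.

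Only the sensitivity analysis in Section 7.3.3 is affected. The reason to act is that no unselected set of infused subjects is named for this endpoint, although one is already defined. Severity: optional improvement.

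**What to change.** In Section 7.3.3, name ITT2 as the population for the sensitivity analysis of the primary safety endpoint. It contains every infused subject whatever the number of cells received, so a stopped infusion cannot change membership. It needs no new definition and no extra data.

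If a PP analysis is kept to describe safety at the target dose, label it supplementary. Beside it, list each infused subject excluded from PP with the reason (product yield or stopped infusion) and whether the endpoint occurred.

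The cost is a change of population in one sentence and, if PP is kept, one extra small table. The PP definition can stay as it is for the efficacy analyses, and no dose or treatment rule changes.

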## **7.4. Secondary Efficacy Endpoints**

All secondary efficacy endpoint analyses will use the ITT2 population, with a sensitivity analysis using the PP population.

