## 1. PROTOCOL SYNOPSIS

Title	Safety of Donor Alloantigen Reactive Tregs (darTregs) to Facilitate Minimization and/or Discontinuation of Immunosuppression in Adult Liver Transplant Recipients ( ARTEMIS )
Short Title	darTregs for CNI Reduction
Protocol Number	CTOTC-12
ClinicalTrials.gov Identifier	NCT02474199
Clinical Phase	Phase I/II
Primary Safety Objective	This study will evaluate the safety and tolerability of a single IV dose of the darTregs product.
Secondary Safety Objective	This study will evaluate the safety of immunosuppression (IS) 1) minimization and 2) discontinuation after one IV dose of darTregs.
Primary Efficacy Objective	The study will evaluate the ability of a single IV dose of darTregs to reduce baseline, standard of care (SOC) calcineurin inhibitor (CNI) dosing by 75% along with discontinuation of either prednisone or mycophenolate mofetil (MMF), as applicable.
Secondary Efficacy Objective	This study will determine whether a single IV dose of darTregs can induce operational tolerance.
Mechanistic Objectives	We will assess the pharmacokinetic profile of darTregs by measuring the level of deuterium-labeled Tregs in circulation. Potential impact of darTregs therapy on immunological profiles will be assessed by comparing leukocyte phenotypes, tissue histology and gene expression in protocol and for-cause biopsies, and alloantibody before and after darTregs infusion.
Study Design	A multi-center, open-label clinical trial in adult liver transplant recipients with two primary interventions: 
 
• administration of a single IV dose of darTregs and
 
• reduction of IS dosing with possible complete IS discontinuation.
 
 Adult living donor liver recipients two to six years after LT will initiate IS withdrawal. Twelve to 14 weeks later, they will receive a single dose of darTregs and continue IS withdrawal.
Primary Safety Endpoint	The safety and tolerability of a single infusion of darTregs administered to LT recipients will be assessed 24 weeks after darTregs by describing: 
 
1. Occurrence of CTCAE Grade 3 or higher adverse events (AEs) attributable to the darTregs infusion including infusion reaction / cytokine release syndrome
 
2. Occurrence of study defined Grade 3 or higher infections
 
3. Occurrence of any malignancy, including PTLD
 

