Secondary Safety Endpoint	The trial will assess the safety of IS withdrawal in the context of darTregs therapy by describing the following secondary safety endpoints: 
 
1. Rate of composite outcome measure including refractory acute rejection, chronic rejection, re- transplantation, and death
 
2. Incidence of biopsy proven or clinical acute rejection and/or chronic rejection
 
3. Timing of biopsy proven or clinical acute rejection and/or chronic rejection
 
4. Severity of biopsy proven acute rejection and/or chronic rejection
 

Primary Efficacy Endpoint	The efficacy of a single IV dose of darTregs will be assessed by the number and proportion of LT subjects who are able to reduce CNI dosing by 75% and discontinue a 2 nd IS drug (if applicable) with stable liver tests for at least 12 weeks. The frequency of successful CNI minimization will be compared to historical cohorts of comparable adult LT recipients undergoing IS withdrawal.
Secondary Efficacy Endpoints	The efficacy of a single IV dose of darTregs infusion will be assessed by determining the number and percentage of subjects who have received darTregs and are identified as operationally tolerant, defined by maintaining stable allograft function (assessed by liver tests) and histology (determined by central pathologist reading in comparison to screening liver biopsy at study entry) in the absence of IS for one year. The frequency of tolerance will be compared to historical cohorts of adult liver transplant recipients undergoing IS withdrawal.
Primary Mechanistic Endpoints	The level and persistence of deuterium-labeled darTregs in the circulation will be determined by serial measurements of deuterium content in DNA from purified peripheral blood Tregs after darTregs infusion using gas chromatography-mass spectrometry (GC-MS) testing.
Secondary Mechanistic Endpoints	The overall increase of darTregs in circulation will be assessed using the alloreactive T cell frequency (ATF) assay

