darTregs Infusion Inclusion Criteria	
Subjects will initiate IS withdrawal and, at the beginning of the 2nd step of the withdrawal algorithm (week 1-2), undergo a final assessment to ensure eligibility for darTregs infusion. Subjects must meet the following criteria to receive darTregs infusion:
 
 
1. Stable liver tests, defined as ALT and either alkaline phosphatase or GGT either within normal limits OR <1.5 X baseline
 
2. No detectable circulating EBV or CMV DNA prior to darTregs infusion, assessed at the time of PBMC collection for manufacture
 
3. For subjects with HBV, no detectable circulating HBV DNA prior to darTreg infusion, assessed at the time of PBMC collection for manufacture
 
4. Able to understand and provide informed consent
 

darTregs Infusion Exclusion Criteria	
Subjects who meet any of these criteria are not eligible for darTregs infusion:
 
 
1. Diagnosis of AR after initiation of IS withdrawal
 
2. Any vaccination given within 28 days prior to Treg collection for Treg production
 
3. Receipt of a vaccination within 14 days prior to Treg infusion
 
4. Unacceptable darTregs product
 
5. Positive pregnancy test
 
6. Clinical evidence of viral syndrome less than 7 days prior to darTregs infusion
 

Field Code Changed

Eligibility Criteria to Resume IS Withdrawal after darTregs infusion	Subjects are eligible to resume IS withdrawal after darTregs infusion if all criteria below are met: 1. Subject received at least $100 \times 10^6$ darTregs 2. ALT and either alkaline phosphatase or GGT remain within normal limits or $\leq 1.5 \times$ baseline after darTregs infusion 3. For subjects with elevated liver tests as defined above, local pathology reading of liver biopsy 6-10 days after darTregs infusion is without acute rejection according to Banff criteria 4. IS withdrawal resumes no later than 14 days after darTregs infusion 5. Site principal investigator determines it is acceptable for the study subject to resume IS withdrawal

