### **7.2.2. Primary Analysis of the Primary Efficacy Endpoint**

The primary efficacy endpoint will be descriptively summarized with an exact binomial proportion and an exact 95% confidence interval using the ITT1 population.

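### Operational tolerance (SAP 7.4.3) is estimated only in subjects who passed a withdrawal run-in, but is to be compared with historical withdrawal cohorts for which no matching landmark is stated

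*SAP*

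**What the plan says.** - **Analysis sets (SAP section 4).** "The Intent-to-treat I sample (ITT1) will be defined as all subjects who initiate IS withdrawal". "The Intent-to-treat II sample (ITT2) will be defined as all subjects who receive darTregs". PP is limited to subjects given at least 300 x 10^6 cells, so it lies inside ITT2.
- **Secondary efficacy (section 7.4).** "All secondary efficacy endpoint analyses will use the ITT2 population, with a sensitivity analysis using the PP population". This covers operational tolerance (7.4.3). No ITT1 analysis is planned.
- **Order of events (section 1, Study Design).** Subjects start withdrawal. "Twelve to 14 weeks later, they will receive a single dose of darTregs and continue IS withdrawal". Infusion falls at the end of withdrawal Step 2, with the CNI reduced by 25% (Treatment Description).
- **Conditions for infusion (section 1).** Liver tests must be stable. One exclusion is "Diagnosis of AR after initiation of IS withdrawal".
- **Comparator (section 1, Secondary Efficacy Endpoints).** "The frequency of tolerance will be compared to historical cohorts of adult liver transplant recipients undergoing IS withdrawal". No run-in, landmark or starting point is given for those cohorts.
- **Contrast.** The primary efficacy endpoint also has a historical comparator in the synopsis. Its main analysis is done "using the ITT1 population" (7.2.2), with ITT2 and PP as sensitivity analyses (7.2.3).

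**The concern.** Tolerance means stable graft function and histology off all IS. A subject who rejects, or whose liver tests become unstable, during the first taper steps has already shown an early form of failure. That subject is not infused and so drops out of ITT2 and PP. The tolerance proportion is therefore conditional on having passed the first part of withdrawal. PP is a subset of ITT2, so the planned sensitivity analysis cannot show the effect of this selection.

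The trial is open-label with no concurrent control, so the stated historical comparison is the main way to read whether darTregs induce tolerance. If the historical proportion includes early rejectors and the trial proportion does not, the trial can look better with no darTregs effect at all.

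**Working it through.** **Inputs.** The set definitions, infusion conditions and comparator are as listed above. The SAP does not give the historical tolerance rate p0, the fraction f of withdrawal starters lost before infusion to rejection or unstable liver tests, or the number m of infused subjects who receive 100–300 x 10^6 cells. All three are assumed below. The SAP states no rate, sample size or test for tolerance, so there is no figure to reproduce. The synopsis also times infusion at about 10–11 weeks (Study Duration row) against 12 to 14 weeks (Study Design row). These must be reconciled, but the argument is the same for either.

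**Step 1: selection alone.** Assume that darTregs have no effect, that subjects lost to rejection or unstable liver tests would never have become tolerant, that other losses are unrelated to tolerance, and that the historical rate p0 is counted from the start of withdrawal. The expected rate among infused subjects is then p0/(1 − f).

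| f | factor 1/(1 − f) | rate if p0 = 0.20 | rate if p0 = 0.30 |
|---|---|---|---|
| 0 | 1.00 | 20.0% | 30.0% |
| 0.10 | 1.11 | 22.2% | 33.3% |
| 0.20 | 1.25 | 25.0% | 37.5% |
| 0.30 | 1.43 | 28.6% | 42.9% |

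**Step 2: the opposite effect in ITT2.** Under the Treatment Description, recipients of 100–300 x 10^6 cells may go only as far as the primary endpoint. They stay in the ITT2 denominator and cannot count as tolerant. With 11 infused, the expected rate becomes p0/(1 − f) × (11 − m)/11. For p0 = 0.30 and f = 0.20:

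- m = 0: 37.5%
- m = 1: 37.5% × 10/11 = 34.1%
- m = 2: 37.5% × 9/11 = 30.7%
- m = 3: 37.5% × 8/11 = 27.3%, now below p0

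The two effects cancel when m = 11f, that is 1.1 subjects at f = 0.10 and 2.2 at f = 0.20. PP excludes these subjects, so it has no such offset.

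**Step 3: what an ITT1 analysis would show.** Suppose 14 subjects start withdrawal, 11 are infused and 4 become tolerant. Of the 3 not infused, 2 had rejection or unstable liver tests and 1 had an unacceptable product. With exact (Clopper-Pearson) 95% intervals:

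- ITT2: 4/11 = 36.4% (10.9 to 69.2)
- ITT1, all non-infused counted as not tolerant: 4/14 = 28.6% (8.4 to 58.1)
- ITT1, the product failure excluded: 4/13 = 30.8% (9.1 to 61.4)

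ITT2 exceeds the last figure by 13/11 = 1.18, which is 1/(1 − f) with f = 2/13. These counts are illustrative only.

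**The case against.** **ITT2 is the denominator that the endpoint defines.** The synopsis counts tolerance among darTregs recipients, and the 7.4.3 title refers to withdrawal after infusion. This stands, and ITT2 should remain the main analysis. The gap lies in setting that proportion against withdrawal cohorts with no landmark stated.

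**The historical denominator is not in the SAP.** This also stands. A reader might infer that the comparison certainly has the wrong denominator. The text supports only that no matching is stated; cohort selection may be set out in the protocol.

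**The direction is not fixed.** A reader might infer that the ITT2 result must favour darTregs. Step 2 shows that low-dose recipients can cancel or reverse the excess. Selection may also be slight, because the run-in reaches only a 25% CNI reduction.

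**Counting every non-infused subject as a failure creates the opposite mismatch.** Infusion can be missed because of an unacceptable product, viral DNA, a vaccination, a viral syndrome or pregnancy. None of these is a withdrawal failure, and product failure cannot occur in a withdrawal-only cohort. So the all-failures ITT1 proportion should not be the sole comparator.

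**Part of this will be visible anyway.** Section 5.1 reports the size of each set, completion of each taper level and reasons for early termination, and section 7.5 analyses rejection incidence in ITT1. A reader could form the all-failures ITT1 proportion. The plan does not commit to it, or to the split by reason that makes it interpretable.

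**Conclusion.** The point holds as a modest, inexpensive improvement. Section 7.4.3 yields a tolerance rate only in subjects who have passed the withdrawal run-in, and the synopsis pairs that rate with historical cohorts without a matching landmark.

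If those cohorts are counted from the start of withdrawal, the factor is 1.11 at f = 0.10 and 1.25 at f = 0.20. It may be close to 1, since the SAP gives no basis for f. The net effect in ITT2 can be smaller, nil or reversed; in PP the selection is not offset in this way.

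Three stronger readings are not supported:

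- **A maximum inflation of 18/11 = 1.64.** Both numbers are upper targets. The 18 are screened and enrolled, so they may include subjects who fail the screening biopsy and never start withdrawal.
- **An inflated type I error.** The SAP sets no test or decision rule for tolerance. The harm would be a misleading descriptive comparison.
- **The same fault in 7.4.1.** The synopsis states no historical comparison for complete withdrawal. An ITT1 proportion there would serve consistency only.

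**What to change.** In section 7.4:

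1. Keep ITT2 as the main analysis of 7.4.3 and PP as a sensitivity analysis.
2. Add an ITT1 sensitivity analysis of 7.4.3, in line with the primary efficacy endpoint, which already uses both ITT1 and ITT2. Tabulate non-infused subjects by reason. Give the exact proportion twice: once with all of them counted as not tolerant, and once with only pre-infusion rejection or unstable-liver-test failures counted as not tolerant and those who missed infusion for other reasons (product, viral, vaccination) excluded.
3. State that when ITT2 or PP is set against history, the historical cohort is restricted to recipients who were rejection-free at the same withdrawal step. If the historical data do not allow this, use the ITT1 figures and state the caveat.
4. Report the number of recipients of 100–300 x 10^6 cells next to the ITT1 and ITT2 proportions, because they sit in both denominators without being allowed to attempt complete withdrawal.
5. Optionally, add an ITT1 proportion for 7.4.1.

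The cost is a few sentences and a few more exact proportions from trial data already collected. Landmark matching also needs taper-step detail from the historical source. The reported tolerance rate may look less favourable.
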